12.1.3 SAMPLE SIZE

A total sample size of up to 350 subjects will provide adequate power to satisfy both the primary efficacy and the safety endpoints respectively. The assumptions and rationale are provided in the sections below.

Clinical Investigational Plan**12.1.4 PRIMARY EFFICACY ENDPOINT**

Assumptions: Based on the analysis of the first 100 subjects enrolled in the PREVENT study (Data on file), the anticipated incidence of non-surgical bleeding in the Control Arm at 6 months is 40%. The assumption for PREVENT II is that there will at least be a 15% reduction in the incidence of non-surgical bleeding in the Treatment Arm compared to the Control Arm.

The comparison of Treatment and Control Arms will be made using the Fishers Exact Test. The primary endpoint for efficacy will be considered to be met if the p -value ≤ 0.05 . A sample size of 330 subjects (165 in each of the Treatment and Control Arms) with an alpha of 0.05 will provide 80% power to demonstrate a significant difference between the Treatment and Control Arms.

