2.3 CLINICAL EQUIPOISE ON THE USE OF ASA IN HM II PATIENTS

The growing body of scientific evidence seems to suggest that ASA therapy in HM II patients may not have an impact on TE events, but may increase the risk of bleeding events in the presence of AVWS. This effect may be particularly accentuated in older patient populations who have higher risk of bleeding (21). The PREVENT recommendations, as well as the HM II IFU, recommend initiation of ASA therapy within 2-5 days post implant, with maintenance of ASA therapy throughout support. Despite these recommendations, clinical experiences from the US and EU cohorts of the TRACE study, as well as single-center experiences in Europe have indicated that ASA therapy may not be required in HM II LVAD patients. Furthermore, in a recent study, the use of high dose ASA therapy (325 mg) was associated with a significantly higher incidence of hemorrhagic events compared to low dose (81 mg) ASA therapy [54% vs. 22%, $p < 0.004$] (32). These results suggest a clinical equipoise for the use of ASA therapy for

Clinical Investigational Plan

antithrombotic management of HM II patients, especially in older patients who are at higher risk of bleeding.

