6.4 BASELINE VISIT

The following baseline assessments will be performed:

Table 2 – Baseline Data Collection

Study Activity	Data Collection
Informed Consent	Informed consent details
Inclusion/Exclusion	Subject's eligibility details
Demographics	Age, gender, ethnicity, race, blood type, INTERMACS profile, and NYHA class
General and Cardiac Medical History	Etiology of HF, duration of HF, indication (BTT/DT), arrhythmias, prosthetic valve(s), stroke, diabetes, smoking, history of bleeding (diverticular disease, diagnosed arteriovenous malformations (AVMs), GI ulcer(s), anemia, and/or erythropoietin treatment), aortic stenosis, hypertension, history of MI, peripheral thromboembolism, coronary stents, CABG, substance abuse (drug/alcohol), drug/radiation toxicity, peripheral vascular disease, carotid artery disease, cardiac rhythm management device, intra-aortic balloon pump, CardioMEMS, and HIV
Vital Signs	Height, weight, blood pressure, and heart rate
Anticoagulation/Antiplatelet Medications	Warfarin, clopidogrel, dipyridamole, other anticoagulation agents, other vitamin K antagonists, direct thrombin inhibitors, etc (including research drug). All new medications started, or current medications stopped during the follow-up period must be recorded. All dose changes (including IV titrations) during the follow-up period must be recorded with the exclusion of Warfarin/Coumadin. Only the start and stop dates will be collected for Warfarin/Coumadin
Other Medications	ACE inhibitors, inotropes, ARBs, beta blockers, antiarrhythmics, statins, nitrates, allopurinol, aldosterone blockers, antibiotics, diuretics, insulin and antidiabetic medications, and other cardiovascular medications
¹ Laboratory Assessments	Hemoglobin (Hgb), Hematocrit (Hct), White Blood Cell Count (WBC), Platelets (PLT), Creatinine (Cr), Estimated Glomerular Filtration Rate (eGFR), LDH and INR. For diabetic patients: HbA1c, and fasting glucose Collected only if SOC: Activated Partial Thromboplastin Time (aPTT), Partial Thromboplastin Time (PTT), Plasma free Hgb (PHgb), liver function tests (AST, ALT, total bilirubin, albumin, pre-albumin), blood urea nitrogen (BUN), D-Dimers, P Selectin, and fibrinogen
ASA Resistance Testing	ASA resistance testing (e.g. TEG® PlateletMapping®, VerifyNow®, etc.) Note: To protect blinding of the study, platelet function testing (including ASA resistance testing) should be avoided during the course of the study except where indicated by the CIP.

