12 STATISTICAL CONSIDERATIONS

PREVENT II is a prospective, multi-center, randomized, double-blinded, placebo-controlled study evaluating the risk of subjects over 50 years of age being managed on warfarin therapy alone compared to warfarin and ASA therapy together. The two groups in the study are as follows:

- 1) Treatment Arm: Warfarin (INR target: 2.0-2.5, median: 2.25) + Placebo (1 pill/day)
- 2) Control Arm: Warfarin (INR target: 2.0-2.5, median: 2.25) + ASA therapy (81mg/day)

In general, continuous data will be presented as the number of subjects, mean with standard deviation, median, minimum, and maximum values. Categorical data will be reported as frequencies and percentages. Adverse events will additionally be reported as events per subject year, with only those events that start after implantation of the HM II analyzed. The adverse events will be compared between the two arms of the study using risk ratios (Poisson's regression). Survival data will be presented and analyzed using the Kaplan-Meier method.

The primary endpoints will be analyzed per protocol method as defined in **Section 12.1**. Every effort will be made to avoid crossovers, but in such instances, analysis will be performed in accordance with **Section 12.1**. The study will be conducted in a double-blinded fashion with neither the investigator, nor the subject having the knowledge of whether the subject is in the Treatment or the Control Arm. Only the primary statistician from the Sponsor will have knowledge of the specific groups, and all other parties will be blinded.

Every effort will be made to collect all required data. A one-sided 0.025 level of significance or two-sided 0.05 level of significance will be used to declare statistical significance as outlined below. Multiplicity adjustments will not be made unless specified below. A sensitivity analysis will be performed to account for any bias that may have been introduced by subjects withdrawing from the study or being removed from the study.

Clinical Investigational Plan**12.1 STATISTICAL DESIGN, HYPOTHESES, METHOD AND ANALYTICAL PROCEDURES**

Subjects will be block randomized per site on a 1:1 ratio into the Treatment and Control Arms. The study is designed to satisfy two primary endpoints. Both primary endpoints must be met for the study to be successful.

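### The primary bleeding test leaves baseline covariates that are already collected unused; a pre-specified adjusted risk difference could add 0 to about 4 points of power (a cheap improvement, not an error)

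*Combined protocol and SAP*

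**What the plan says.** Section 12.1.4 names the primary efficacy test: "The comparison of Treatment and Control Arms will be made using the Fishers Exact Test". The synopsis names the same test. On design assumptions, section 12.1.4 says "the anticipated incidence of non-surgical bleeding in the Control Arm at 6 months is 40" (per cent) and that "there will at least be a 15% reduction in the incidence of non-surgical bleeding in the Treatment Arm". The size follows: "A sample size of 330 subjects (165 in each of the Treatment and Control Arms"), which "with an alpha of 0.05 will provide 80% power to demonstrate a significant difference". On sidedness, section 12 says: "A one-sided 0.025 level of significance or two-sided 0.05 level of significance will be used".

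No covariate appears in any primary analysis. Section 12 adds Poisson risk ratios for adverse events, Kaplan-Meier for survival and a sensitivity analysis for withdrawals, none with named covariates. Randomisation is stratified by site alone (section 12.4).

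Table 2 in section 6.4 records age, hemoglobin and eGFR before implant, and an itemised "history of bleeding (diverticular disease, diagnosed arteriovenous malformations (AVMs), GI ulcer(s), anemia, and/or erythropoietin treatment"). Section 2.3 argues that equipoise exists "especially in older patients who are at higher risk of bleeding".

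**The concern.** If the baseline variables predict bleeding, an unadjusted test leaves variation they could explain in the error term. With stratification by site only, a chance imbalance in prior bleeding could also be offered afterwards to explain either result. A covariate list fixed in advance answers that; one chosen after unblinding does not.

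The margin is thin. Success requires both primary endpoints, each sized for 80% power. If the two were independent (an assumption), joint power would be 0.80 × 0.80 = 64%. Enrolment is up to 350 against requirements of 330 and 338, withdrawn subjects are not replaced (section 4.2), and the primary analysis is per protocol (section 12). A few points of power without extra subjects are therefore worth having.

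**Working it through.** **Inputs from the plan.** Control rate 40%, reduction 15%, alpha 0.05, 165 per arm (section 12.1.4); 175 per arm planned (synopsis). **Not in the plan:** how strongly the covariates predict bleeding. This is varied below.

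**1. Reproduce the stated size.** Take the reduction as absolute (40% against 25%), so the mean rate is 0.325.

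n₀ = [1.960·√(2·0.325·0.675) + 0.842·√(0.40·0.60 + 0.25·0.75)]² / 0.15² = (1.298 + 0.550)² / 0.0225 ≈ 152 per arm.

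With continuity correction, n = (n₀/4)·[1 + √(1 + 4/(0.15·n₀))]² ≈ 165 per arm, which matches the plan. A relative reduction (40% to 34%) would need 1,016 to 1,049 per arm, so the absolute reading is the plan's.

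**2. Power of the planned test.** Summing the two binomial probabilities over every table with a two-sided Fisher p-value of at most 0.05 gives 80.5% at 165 per arm and 82.5% at 175. The actual size is 3.88% at a common rate of 32.5% with 165 per arm, and 3.8% to 3.9% at 25%, 32.5% and 40% for either sample size.

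**3. Gain from leaving Fisher, with no covariates.** The large-sample test has power Φ{[0.15·√n − 1.298]/0.654}. At n = 165 this is Φ(0.961) = 83.2%, a gain of 83.2 − 80.5 = 2.7 points.

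**4. Gain from covariates, by formula.** If covariates explain a share R² of outcome variance, replace n by n/(1 − R²).

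| Assumed R² | Power, 165 per arm | Gain over 83.2% |
|---|---|---|
| 2% | 83.9% | +0.7 |
| 3% | 84.3% | +1.1 |
| 5% | 85.0% | +1.9 |
| 10% | 86.9% | +3.7 |

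At 175 per arm the unadjusted figure is 85.3%; R² of 5% gives 87.0% (+1.7) and 10% gives 88.8% (+3.5).

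**5. Gain from covariates, by simulation.** Bleeding follows a logistic model with a normal prognostic index of standard deviation SD, and arm intercepts set so that the marginal rates stay at 40% and 25%. The adjusted test is a logistic fit standardised over all subjects, with an influence-function variance. At 165 per arm, 4,000 runs:

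| SD | AUC | Fisher | Unadjusted | Adjusted | Covariate gain | Gain in a separate simulation |
|---|---|---|---|---|---|---|
| 0 | 0.50 | 79.6% | 82.9% | 82.9% | 0.0 | about 0 |
| 0.4 | 0.61 | 81.4% | 84.4% | 85.1% | +0.7 | +1.5 |
| 0.6 | 0.66 | 80.3% | 83.6% | 85.6% | +2.0 | +2.9 |
| 0.8 | 0.70 | 80.3% | 83.5% | 87.2% | +3.7 | +4.0 |

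The marginal rates are fixed, so the spread in the Fisher column is simulation error: √(0.8·0.2/4,000) ≈ 0.6 points per entry.

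A larger simulation (15,000 runs, 165 per arm) gave 84.1% to 83.5% with no prognostic value, 83.8% to 84.9% (+1.1) at SD 0.5 (R² about 5%), and 84.1% to 86.8% (+2.6) at SD 0.7 (R² about 9%).

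**6. Size of the adjusted test.** In 20,000 null runs per setting, two-sided size was 5.1% to 5.5%. Other simulations gave 4.6% to 5.5% and 5.2% to 5.7%.

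**7. Why a cushion helps.** The plan gives no loss rate, so take 10% and 15% as illustrations: 175 × 0.90 ≈ 157 and 175 × 0.85 ≈ 149 per arm. Fisher power falls to 78.0% and 76.1%. At 149 per arm the large-sample test has 79.2% unadjusted, 81.3% with R² of 5% and 83.3% with 10%.

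**The case against.** Fisher's test is valid in a 1:1 randomised trial. Its type I error already allows for chance imbalance, and it delivers the power the plan promises. All of this stands, so the point is missed efficiency.

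A reader might infer that the trial discards strong predictors and certainly forfeits 2 to 4 points. The documents do not support that. Only age is described as a bleeding risk factor, and entry at 50 years or older narrows its range. No AUC, R² or odds ratio is given for any variable. The bleeding-history item includes anemia and erythropoietin treatment, so it overlaps with hemoglobin, and four entries are not four independent predictors. At low prognostic strength the gain is about 1 point or nothing.

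Some of the apparent advantage also reflects size. The adjusted test ran slightly above 5% in most simulations, while Fisher's runs near 3.9%. In one simulation with size matched, the covariate gain at SD 0.6 fell from 3.1 to 2.1 points. The gain shrinks but remains.

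It is also tempting to carry the model over to the safety endpoint, adding prior stroke. At 8% and 9% with 169 per arm, about 169 × 0.08 + 169 × 0.09 ≈ 29 events are expected, against six or more parameters. A check at the 10-point margin (8% against 18%) gave an adjusted Wald-type one-sided size of 2.9% to 3.6% against 2.5%. That would replace the Farrington-Manning approach of section 12.1.5 with a more liberal test of the safety claim, so the extension is not recommended.

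**Conclusion.** The point holds as a low-cost improvement. The planned test meets its stated 80% power and contradicts nothing in the plan. Pre-specified adjustment would add 0 to about 4 points from the covariates, assuming their joint AUC lies between 0.5 and 0.70; the documents give no figure to narrow this. About 3 further points (2.7 by formula, 3.3 in the simulation at AUC 0.66: 83.6 − 80.3) come from leaving Fisher's conservatism and should not be credited to the covariates. If the covariates carry no information, the cost in power is negligible. The practical value is a cushion against unreplaced withdrawals and a ready answer to chance imbalance. A reader should not conclude that the trial is underpowered as planned, or that a particular number of points is being lost.

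**What to change.** In section 12.1.4 and the synopsis, make the primary efficacy analysis a covariate-adjusted risk difference:

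- Fit a logistic model with arm, age, any prior bleeding history, baseline hemoglobin and eGFR.
- Standardise the predictions (g-computation) over all subjects in the primary analysis set, with robust variance, and test at two-sided 0.05.
- Fix the covariate list and coding before any unblinding.
- State a simple rule for missing baseline values that does not depend on arm.
- State how site is handled. It is the only stratification factor, and up to 45 sites for 350 subjects means about 350/45 ≈ 8 per site, which is sparse for a separate term per site.
- Keep the unadjusted Fisher test as a sensitivity analysis.
- If an exact test is wanted, specify a re-randomisation p-value that follows the site-blocked allocation. This also addresses the slight excess in size.

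Leave the safety analysis on the Farrington-Manning approach.

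Cost: a paragraph of text and slightly more programming, with no new data, visits or subjects. Without re-randomisation the test is no longer exact, and its size may run at about 5.0-5.5%.

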12.1.5 PRIMARY SAFETY ENDPOINT

Assumptions: Based on the analysis of the first 100 subjects enrolled in the PREVENT study (Data on file), the anticipated composite incidence of TE events in the Control Arm at 6 months is expected to be 8%. The assumption for PREVENT II is that the Treatment Arm will experience an incidence of TE events of no more than 9% at 6 months. The Treatment Arm will be considered non-inferior to the Control Arm if the upper one-sided 95% confidence limit of the risk difference in the 6 month TE rate between research drug arms (Treatment - Control) is less than +10% ("positive 10%", where 10% is the non-inferiority Δ in the above null and alternative hypotheses).

A sample size of 338 subjects (169 each in the Treatment and Control Arms) will achieve 80% power to prove the Treatment Arm is non-inferior to HM II when the margin of non-inferiority is 10% ($=\Delta$ in the above null and alternative hypotheses) using the Farrington-Manning risk difference approach to non-inferiority at a one-sided alpha = 0.025.

[figure not shown]

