Maximum follow-up duration per subject will be 12 months. Primary endpoints will be evaluated at 6 months. Individual components of the primary endpoints along with the descriptive endpoints will be evaluated at 12 months.

Clinical Investigational Plan

Study Synopsis

Statistical Considerations	
Primary Efficacy Endpoint Analysis – Reduction of Bleeding: The rate of non-surgical bleeding at 6 months will be compared between the Treatment and Control Arms utilizing the Fisher’s Exact Test. The primary endpoint for efficacy will be assumed to be met if the p-value < 0.05. The assumption is that there will be a 15% rate reduction at 6 months.
 
A sample size of 330 subjects (165 in each arm) with an alpha of 0.05 will provide 80% power to demonstrate a significant difference between the Treatment and Control Arms.
 
Primary Safety Endpoint Analysis – Non-Inferiority of Stroke and Thrombus: The difference in the rates of the composite endpoint of stroke and pump thrombosis between Treatment and Control Arms and the 95% confidence limit of the difference will be evaluated. If the upper confidence limit of the difference is < 10% then the non-inferiority criterion will be considered to have been met.
 
A sample size of 338 subjects (169 in each arm) will provide 80% power, with a target alpha of 0.025 (because this will be a one-sided test on the upper confidence limit) to demonstrate non-inferiority of the Treatment Arm to the Control Arm.
 
A total study sample size of 350 subjects will provide enough statistical power to demonstrate both efficacy and safety of the warfarin only anticoagulation regimen in these patients.
 
Both primary endpoints must be met for the study to be successful.
 
Intermediate Safety Assessment: A safety assessment will be performed after 60 subjects have completed 3 months of follow-up. Both incidence of stroke and pump thrombosis will be analyzed and results will be presented to the Steering Committee. Additionally, after the initial 3-month safety review, an analysis of AEs associated with primary endpoints will be presented to the Steering Committee for continued safety assessment in regular 6-month intervals. The Steering Committee will review the findings and make a decision to proceed or stop the study due to safety concerns.

Devices Used	HM II Left Ventricular Assist Device (LVAD)

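### The non-inferiority rule in Section 12.1.5 works at one-sided 0.05, while the stated alpha and the sample size are one-sided 0.025

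*Combined protocol and SAP*

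**What the plan says.** Four places bear on the significance level of the primary safety test.

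- **Section 12.1.5, decision rule.** Non-inferiority is declared if the "upper one-sided 95% confidence limit of the risk difference in the 6 month TE rate between research drug arms" (Treatment minus Control) is less than +10%.
- **Section 12.1.5, sample size.** The 169 per arm for 80% power is obtained "using the Farrington-Manning risk difference approach to non-inferiority at a one-sided alpha = 0.025".
- **Section 12, general.** "A one-sided 0.025 level of significance or two-sided 0.05 level of significance will be used to declare statistical significance as outlined below".
- **Synopsis, Statistical Considerations.** The sizing sentence works "with a target alpha of 0.025 (because this will be a one-sided test on the upper confidence limit"). The rule itself refers to a 95% confidence limit without giving its sidedness, then says: "If the upper confidence limit of the difference is < 10% then the non-inferiority criterion will be considered to have been met".

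The efficacy text is also loose. Section 12.1.1 states a one-sided alternative, and Section 12.1.4 says "A sample size of 330 subjects (165 in each of the Treatment and Control Arms) with an alpha of 0.05 will provide 80% power" without saying whether that alpha is one-sided or two-sided.

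**The concern.** A one-sided 95% upper limit lies 1.645 standard errors above the estimate, and requiring it to fall below the margin is a test at one-sided alpha 0.05. A test at one-sided 0.025 needs the one-sided 97.5% limit, which is the upper end of a two-sided 95% interval, at 1.960 standard errors. Section 12.1.5 therefore gives two different alphas for one test in consecutive paragraphs. Section 12 does not settle it, because it refers the reader to Section 12.1 for the primary analyses, and the only rule there with a stated sidedness is the looser one.

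This rule decides whether leaving out aspirin can be called safe for pump thrombosis and stroke, and both primary endpoints must be met for the study to succeed. A success criterion that can be read two ways allows the choice to be made after the data are known.

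**Working it through.** **Inputs, all from Section 12.1.5 unless noted.** Control rate 8%, Treatment rate 9%, margin 10 percentage points, 80% power, 169 per arm. Planned enrolment is 175 per arm (synopsis). The null is taken as a true excess of 10 points or more, as the decision rule implies.

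**Step 1: reproduce the plan's sample size.** The Farrington-Manning formula is

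n per arm = [(z(1−α)·s0 + z(0.80)·s1) / (0.10 − 0.01)]²

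- s1 uses the assumed rates: √(0.09×0.91 + 0.08×0.92) = √0.1555 = 0.3943.
- s0 uses the rates fitted by maximum likelihood under a 10-point difference, 15.45% and 5.45%: √(0.1545×0.8455 + 0.0545×0.9455) = 0.4269.
- z(0.80) = 0.8416.

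| One-sided α | z(1−α) | n per arm | Power at 169 per arm | Power at 175 per arm |
|---|---|---|---|---|
| 0.025 | 1.960 | (1.1685/0.09)² = 168.6, so 169 | 80.1% | 81.5% |
| 0.05 | 1.645 | (1.0340/0.09)² = 132.0, so 132 | 88.2% | 89.2% |

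The stated 169 per arm matches 0.025 and not 0.05. An unpooled-variance formula gives 151 and 119 per arm, so neither of its results explains 169.

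**Step 2: false non-inferiority under each rule.** Exact binomial enumeration at the margin, Treatment 18% and Control 8%:

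| Method | n per arm | One-sided 97.5% limit | One-sided 95% limit (as written) |
|---|---|---|---|
| Farrington-Manning | 169 | 2.49% | 4.86% |
| Farrington-Manning | 175 | 2.40% | 5.06% |
| Wald | 169 | 2.81% | 5.50% |
| Wald | 175 | 2.85% | 5.39% |

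The written rule raises the error by a factor of about 1.9 to 2.1. Wald is included because the plan names Farrington-Manning for the sample size but names no method for the confidence limit.

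**Step 3: the gap in events.** Largest Treatment Arm count that still passes, shown as the 97.5% limit against the 95% limit:

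| Control events | Farrington-Manning, 175 per arm | Wald, 175 per arm | Farrington-Manning, 169 per arm |
|---|---|---|---|
| 7 | 14 vs 16 | 15 vs 16 | 14 vs 15 |
| 14 | 20 vs 21 | 20 vs 22 | 19 vs 21 |
| 17 | 22 vs 24 | 22 vs 24 | 22 vs 23 |

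As an example, take 14/175 (8.0%) in Control and 21/175 (12.0%) in Treatment. The difference is 4.0 points, the Farrington-Manning statistic is −1.80 and the one-sided p-value is 0.036. This passes at 0.05 and fails at 0.025.

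**Step 4: efficacy.** Reading the assumed 15% reduction as absolute (40% to 25%), Fisher's exact test with 165 per arm has 80.5% power at two-sided 0.05 and 87.9% at one-sided 0.05. The stated 80% therefore fits two-sided 0.05.

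**The case against.** The best defence is that the intent can be recovered. Three statements give 0.025, the sample size agrees with them, and the synopsis's unsided 95% limit can be read as the upper end of a two-sided 95% interval. On that reading, the word one-sided in Section 12.1.5 is a slip. This is probably how the sentence arose, but it does not remove the conflict: the plan then holds one rule in the synopsis and a different one in the section that defines the analysis.

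Three limits on the size of the problem do stand.

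- The doubling occurs only if Section 12.1.5 is executed literally, and it is calculated with the true excess at the 10-point margin.
- The two rules differ by only one or two Treatment Arm events. The exact counts depend on the interval method and on how many subjects are analysed. The primary analysis is per protocol and withdrawals are not replaced, so fewer than 175 per arm is likely. The counts are illustrative.
- Because both primary endpoints must be met, the chance of a false overall success cannot exceed the error of the safety test alone.

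On efficacy the objection largely succeeds. Section 12 allows only one-sided 0.025 or two-sided 0.05, so an unqualified 0.05 resolves to two-sided, and the power figure confirms it. A clarifying phrase is enough.

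**Conclusion.** The concern holds. The written success criterion for the primary safety endpoint contradicts the plan's own alpha and its own sample size. Followed literally, it raises the nominal one-sided error from 0.025 to 0.05; by exact calculation with Farrington-Manning at 175 per arm, from 2.4% to 5.1%. These figures assume a Control rate of 8%, a true excess of 10 points and all 175 per arm analysed; the ratio is much the same at 169 per arm or with a Wald limit. The practical band is narrow, but it lies on the decision boundary of an endpoint that determines whether the study succeeds, so it must be closed before treatment assignments are unblinded for analysis. The efficacy wording is a minor companion point.

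**What to change.** - **Section 12.1.5 and synopsis.** State one rule in identical words: the Treatment Arm is non-inferior if the upper limit of the two-sided 95% confidence interval (equivalently, the one-sided 97.5% upper limit) for the Treatment minus Control risk difference, calculated by the Farrington-Manning method, is less than +10 percentage points.
- **Section 12.1.4 and synopsis.** State that Fisher's exact test is two-sided at 0.05 and that success also requires the lower bleeding rate to be in the Treatment Arm (equivalent to one-sided 0.025).

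The cost is wording only. The sample size was already computed at 0.025, and power for the safety endpoint is 80.1% at 169 per arm and 81.5% at 175 per arm. Compared with the rule as now written, the Treatment Arm is allowed one or two fewer events.
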